1 SUMMARY

Patiromer add-on to an MRA in patients with Type 2 diabetes mellitus and CKD will reduce blood pressure and LV mass to a greater extent compared to patients with MRA alone and favorably affect key secondary hemodynamic and inflammatory variables including atherosclerosis progression.

Atherosclerosis is the leading cause of morbidity and mortality in Type II diabetes. A cell type called the monocyte/macrophage is critical to development and complications of atherosclerosis.

This project will evaluate the effectiveness of a medication called Spironolactone in addition to Patiromer in preventing atherosclerosis in Type II diabetes through its effects on cells such as the monocyte.

Spironolactone has been demonstrated to be effective for the treatment of patients after a heart attack and stroke. We will evaluate the impact of Spironolactone in combination with Patiromer in reducing atherosclerosis plaque and additionally evaluate its potential in changing inflammation.

We envision that our strategy of simultaneously probing effect of a drug combined with analysis of mechanisms of action and predictive response will likely provide key information with which to design hard event (heart attack, stroke etc.) based trials.

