3 STUDY RATIONALE

There is substantial interest in preventing CV and renal disease progression in the Type 2 diabetic. Activation of the renin angiotensin aldosterone axis (RAS) and the mineralocorticoid receptor (MR) results in pro-inflammatory effects. Further the phenomenon of aldosterone escape provides a rationale for MR antagonism in addition to an ACEI/ARB agent. Agents that target the RAAS cascade have shown benefit in Type 2 Diabetics although combined RAS blockade such as using ACEI+ARB or ACEI/ARB+Renin inhibition have met with failure primarily owing to adverse effects such as hypotension and renal failure/hyperkalemia requiring dialysis. It has been speculated that dual RAS blockade or use of ACEI/ARB in conjunction with MRA may potentially be beneficial if one controls hyperkalemia and/or avoid excess hypotension. As a foundation for this current proposal, we have demonstrated an important role for RAAS and MR antagonism in reducing atherosclerosis and inflammation in experimental animal models and limited studies in humans. We are currently testing the efficacy of Spironolactone in reducing atherosclerosis on top of ACEI/ARB in high-risk patients with T2DM with concomitant CKD as part of a Randomized Double-blind controlled clinical

trial. Given the fact that as much as 20-40% of a diabetic patient population with CKD may have problems of hyperkalemia on spironolactone, particularly those already on ACEI/ARB therapy, that would preclude their participation in this trial, we would like to propose an open label supplemental arm to where in patients who are ineligible for participation owing to baseline hyperkalemia or hyperkalemia on the dose escalation phase will be eligible to participate in the PRIMARY-Add on trial. The addition of Patiromer will enable introduction of MRA therapy at therapeutic doses and avoidance of hyperkalemia. We thus propose a prospective open label trial with blinded assessment of end-points (PROBE) study which test the relative safety and efficacy of Patiromer on top of Spironolactone in T2DM on LV mass regression and occurrence of hypokalemia (Co-Primary End-points) as well as its effect on 24-hour ABP at 6 weeks, central aortic blood pressure at 6 weeks, atherosclerosis progression at 12 months and measures of monocyte inflammatory potential. If successful, the studies outlined in this proposal will extend the utility of Patiromer in high-risk diabetics at risk for future CV events and provide new information.

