3.1.2 Potential Benefits of the Proposed Research to the Subjects and Others

It is possible that there may be a benefit with Spironolactone in terms of organ protection and patients may see benefits relating to reduction of atherosclerotic plaque including reduction in risk for events such as heart attacks, stroke, renal failure and need for hospitalization. The potential benefits must obviously be contrasted with the risk for renal failure and hyperkalemia. Adding Patiromer to Spironolactone in patients with Type 2 diabetes mellitus and chronic kidney disease may reduce blood pressure and left ventricular mass to a greater extent compared to patients with Spironolactone alone, and favorably affect key secondary hemodynamic and inflammatory variables including atherosclerosis progression.

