4. STUDY OBJECTIVES

4.1 Primary Objective

Specific Aim 1: To conduct a prospective open label proof-of-concept clinical trial in 50 patients with Type II diabetes evaluating the effects of MRA + Patiromer on LV mass and plaque regression over 12 months of treatment by MRI. Primary outcome measures will be change in LV mass of patients receiving Patiromer + Spironolactone at the end of 12 months and end-point of safety during this period. An additional co-primary measure will include percent change in atheroma volume (PAV) in the thoracic aorta on Patiromer + Spironolactone at the end of 12 months. Additional secondary measures will include central aortic blood pressure, 24-hour mean systolic blood pressure and measures of insulin resistance (HOMA-IR) at 12 weeks.

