4.2 Secondary Objective

Specific Aim 2: To compare monocyte polarization and inflammatory activation (flow cytometry and gene expression) after 6 weeks of Patiromer therapy. Specific Aim 2b: Results from this aim will help provide insights into mechanisms of disease progression and preservation of pathways by Patiromer.

[figure not shown]

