5. STUDY DESIGN

OVERALL STUDY DESIGN AND EXECUTION

This will be a multicenter trial that will provide a logical extension to a recently funded NIH sponsored trial to assess efficacy of Spironolactone in patients with Type 2 DM and CKD (GFR 20-90ml/m²) compared to placebo (NCT02169089). In this extension study to

NCT02169089, patients with GFR 20-70 ml/m² who are hyperkalemic at baseline (with or without RAAS therapy) precluding an MRA and/or develop hyperkalemia on an MRA (**FIGURE 3**) will be enrolled and placed on Spironolactone. The primary efficacy variables being LV mass change and in patients treated with Patiromer and MRA. Our hypothesis is that Patiromer use in conjunction with an MRA will result in more effective blood pressure lowering, LV mass regression and plaque regression due to more effective lowering of aldosterone and inflammation. The primary safety variable is development of serious hyperkalemia on treatment in Patiromer+Spironolactone arm. Several secondary variables will be obtained, including monocyte-macrophage inflammatory indices, central aortic blood pressure and 24-hour blood pressure at 6 weeks and arterial compliance.

Figure 3.

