9.3.2 Formulation of Control Product

There is no control product in this research protocol.

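### The Summary claims more benefit than an MRA alone and Aim 2 credits patiromer, but every patient gets both drugs and no MRA-alone comparison is specified

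*Combined protocol and SAP*

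**What the plan says.** - **Comparative claim.** Section 1 states that patiromer added to an MRA "will reduce blood pressure and LV mass to a greater extent compared to patients with MRA alone". Section 3.1.2 (Potential Benefits) is softer: the addition "may reduce blood pressure and left ventricular mass to a greater extent compared to patients with Spironolactone alone". Section 5 hypothesises that the combination "will result in more effective blood pressure lowering, LV mass regression and plaque regression", naming no comparator.
- **Attribution.** Section 4.2 studies monocytes after 6 weeks of patiromer and expects insight into "mechanisms of disease progression and preservation of pathways by Patiromer".
- **Treatment.** Sections 9.1 and 9.3.3 put every patient on both drugs. Section 9.3.2: "There is no control product in this research protocol".
- **Objective.** Section 4.1: "Primary outcome measures will be change in LV mass of patients receiving Patiromer + Spironolactone at the end of 12 months".
- **Link to another trial.** Section 5 calls this an extension of a "recently funded NIH sponsored trial to assess efficacy of Spironolactone in patients with Type 2 DM and CKD", which compared spironolactone with placebo. Sections 2 and 3 call it a supplemental arm for "patients who are ineligible for participation owing to baseline hyperkalemia or hyperkalemia on the dose escalation phase".
- **PAV.** Section 6.1 writes its plaque formulas for a spironolactone group and a placebo group, and adds a normalised volume change that uses the other group's median slice count.
- **Reading.** Sections 2 and 3 promise blinded end-point assessment; section 9.2 says that the protocol is not blinded. Section 6.1 has LV contours corrected by hand and plaque areas measured by hand on co-registered baseline and follow-up images.

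**The concern.** A claim of greater effect than MRA alone needs an estimate of what happens on MRA alone. A claim about patiromer needs a contrast in which patiromer is what differs. Neither is specified. A change from Visit 2 mixes patiromer, spironolactone, the passage of time and regression to the mean. If the wording stays, a before-after change on two drugs could be reported as the added benefit of one of them. The PAV text matters because PAV is a co-primary measure. Scan order matters because a reader's tendency to trace follow-up scans differently would not cancel when there is no second arm.

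**Working it through.** **1. Is there an MRA-alone reference inside the study?** Inputs are sections 9.1, 9.3.3 and the schedule in 11.1.1. I assume that Visit 2 (W5) closes the run-in. The schedule suggests this, but the table is broken in the text available.

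| Source | Screening K (mEq/L) | Spironolactone alone before Visit 2 | Patiromer alone before Visit 2 | Started at Visit 2 |
|---|---|---|---|---|
| 9.3.3 | 4.6–5.2 | 1 week | 0 | patiromer |
| 9.3.3 | 5.3–5.5 | 0 | 0 | both |
| 9.3.3 | >5.5 | 0 | 2 weeks | spironolactone |
| 9.1 | all | 0 | 2 weeks | spironolactone |

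The two sections disagree on what is given first. Under either, Visit 2 is neither a uniform drug-free baseline nor an MRA-alone baseline. Change from Visit 2 runs to Visit 6 over 11 − 5 = 6 weeks and to Visit 8 over 53 − 5 = 48 weeks. No study MRI is scheduled before Visit 2, so the 1-week spironolactone run-in yields no MRA-alone change in LV mass or PAV.

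**2. Is there one outside the study?** The parent trial has a spironolactone arm, but neither section 5 nor section 15 writes a contrast with it. Such a contrast would not be randomised. Patients here are described as those whom hyperkalemia kept out of the parent trial; entry requires K of at least 4.6, and section 5 gives GFR 20–70 here against 20–90 there.

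**3. What can be estimated?** Mean within-patient change. Its 95% CI half-width, in SDs of that change, is t(0.975, n−1)/√n:

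- n = 50: 2.010/7.071 = 0.284
- n = 20: 2.093/4.472 = 0.468
- n = 10: 2.262/3.162 = 0.715

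Fifty is the planned maximum. The other two are assumed values, because enrolment is permanently closed (COVID-19 plan, section 11.3) and the achieved number is not given.

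**4. Does PAV need a second group?** By Formula 2, TPV = Z × (N_median/N_patient) × TPA. If both visits use the same slices, the multiplier is the same at baseline and follow-up, so

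(TPV_post − TPV_base)/TPV_base = (TPA_post − TPA_base)/TPA_base.

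The group median drops out. In one simulated group of 50 (invented data), setting the median to 40, 50 or 56 slices left PAV at −3.20% each time, while absolute ΔTPV moved from −2.47 to −3.46. So PAV is computable in one arm. Only the additional normalised ΔTPV has a term that does not exist here.

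**5. Is Formula 3B consistent?** It sets the mean of patient ratios equal to group change over group baseline (which I read as the group mean). Take two invented patients, with TPV 100 falling to 90 and 50 staying at 50:

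- mean of ratios: 100 × ½ × (−10/100 + 0/50) = −5.0%
- ratio of means: 100 × (−5)/75 = −6.7%

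The two sides generally differ. In the simulated group they were −3.20% and −3.16%, so the gap can also be small.

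**6. Scan order.** Section 6.1 describes hand correction and hand tracing, and states no removal of dates, no random presentation and no locking of contours.

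**The case against.** The operative objective in section 4.1 is already a proof-of-concept change on the combination, and no written analysis depends on the comparative sentence. That stands, and it limits the severity: the primary estimand does not change.

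A reader might infer that the comparison can never be made. The documents do not go that far. The supplemental-arm wording and the leftover spironolactone and placebo groups make a contrast with the parent trial a plausible intention; section 15 defers the analyses to a SAP still to be written, and Figure 3 is not shown. Some patients with K 4.6–5.0 are also below the protocol's own threshold for mild hyperkalemia (above 5.0, section 2.1), so the populations may overlap. What holds is that no contrast is specified and that it would be non-randomised and not like-for-like.

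Four other stronger readings also fail:

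- That section 5 claims superiority over MRA alone: its hypothesis names no comparator.
- That PAV cannot be computed in one arm: step 4 shows that it can.
- That exact weeks on each drug at Visit 6 are known: this rests on inferred visit timing, and section 9.3.3 gives the middle stratum no run-in. It also leaves out patients who come in after hyperkalemia on an MRA (section 5) and so have earlier MRA exposure.
- That scans are read unmasked or with bias: open-label treatment is compatible with blinded reading, blinded assessment is promised, and the manual of operations cited in 6.1 was not available. Only the absence of a stated step is established.

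**Conclusion.** The point holds as a mismatch between claim and design, and should be fixed. Sections 1 and 3.1.2 state or suggest a benefit over MRA alone, and section 4.2 attributes findings to patiromer; nothing specified can support either. The supportable estimand is within-patient change on the combination, with a CI half-width of about 0.28 SD at 50 patients and wider if fewer were enrolled. The size of any difference from MRA alone cannot be derived from the documents.

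The statement about Visit 2 assumes that it closes the run-in. The PAV cancellation assumes the same slices at both visits. The scan-order point is secondary; neither the size nor the direction of any reading effect can be given.

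**What to change.** 1. **Hypothesis.** In sections 1 and 3.1.2, and for clarity in 5, write: 'Within-patient change in LV mass and PAV (Visit 2 to Visit 8) and in 24-hour BP (Visit 2 to Visit 6) on spironolactone + patiromer, with 95% CI. No comparison with MRA alone is made.' Describe the run-in actually received before Visit 2; keep this descriptive, as cells may be small. In 4.2 write 'change on spironolactone + patiromer' and delete the clause crediting patiromer with preserving pathways. Label any contrast with the parent trial's spironolactone arm exploratory and non-randomised. Carry all this into the SAP.
2. **PAV.** Define it as the mean over patients of 100 × (TPV_post − TPV_base)/TPV_base. Drop the second equality in Formula 3B, the spironolactone/placebo wording and the normalised ΔTPV formula.
3. **Reading.** For scans not yet read, remove dates and visit labels, present each patient's scans in random order and lock contours before unmasking. If the manual of operations already covers this, cite it.

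The cost is wording edits, a one-line formula and some image handling, with no new patients or scans. A control arm is not proposed, because enrolment is closed. The downside is a weaker, non-comparative claim.

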2 BACKGROUND

[figure not shown]
Hyperkalemia is a condition that frequently occurs in patients with Type 2 Diabetes with chronic kidney disease (CKD). Patients at the highest risk for hyperkalemia are those taking renin-angiotensin-aldosterone system (RAAS) inhibitors with stage 3 or higher CKD. Clinicians frequently either avoid using RAAS inhibitors or use them at lower than recommended doses in these patient populations and as a consequence these patients, who are often the highest risk from a cardiovascular (CV) and renal disease perspective are often not on RAAS antagonists and/or blockers of the mineralocorticoid receptor (MR). Patiromer is an orally administered drug approved for the treatment of hyperkalemia. The active moiety, a nonabsorbed polymer that binds potassium in the gastrointestinal tract, increases fecal excretion of potassium and lowers serum potassium levels. Previous Phase 2 and 3 studies in the CKD population and those with concomitant Diabetes and CKD population have demonstrated the safety of this drug and the ability to introduce RAAS antagonists without fear of precipitating hyperkalemia. Additionally, continued lowering of blood pressure along with reduction in aldosterone levels have been demonstrated. There is substantial interest in preventing CV and renal disease progression in the Type 2 diabetic. Activation of the renin angiotensin aldosterone axis (RAS) and the mineralocorticoid receptor (MR) results in pro-inflammatory effects. Further the phenomenon of aldosterone escape provides a rationale for MR antagonism in addition to an ACEI/ARB agent. Agents that target the RAAS cascade have shown benefit in Type 2 Diabetics although combined RAS blockade such as using ACEI+ARB or ACEI/ARB+Renin inhibition have met with failure primarily owing to adverse effects such as hypotension and renal failure/hyperkalemia requiring dialysis. It has been speculated that dual RAS blockade or use of ACEI/ARB in conjunction with MRA may potentially be beneficial if one controls hyperkalemia and/or avoid excess hypotension. As a foundation for this current proposal, we have demonstrated an important role for RAAS and MR antagonism in reducing atherosclerosis and inflammation in experimental animal models and limited studies in humans. We are currently testing the efficacy of Spironolactone in reducing atherosclerosis on top of ACEI/ARB in high-risk patients with T2DM with concomitant CKD as part of a Randomized Double-blind controlled clinical trial. Given the fact that as much as 20-40% of a diabetic patient population with CKD may have problems of hyperkalemia on spironolactone, particularly those already on ACEI/ARB therapy, that would preclude their participation in this trial, we would like to propose an open label supplemental arm to where in patients who are ineligible for participation owing to baseline hyperkalemia or hyperkalemia on the dose escalation phase will be eligible to participate in the PRIMARY-Add on trial. The addition of Patiromer will enable introduction of MRA therapy at therapeutic doses and avoidance of hyperkalemia. We thus propose a prospective open label trial with blinded assessment of end-points (PROBE) study which test the relative safety and efficacy of Patiromer on top of Spironolactone in T2DM on LV mass regression and occurrence of hypokalemia (Co-Primary End-points) as well as its effect on 24-hour ABP at 6 weeks, central aortic blood pressure at 6 weeks, atherosclerosis progression at 12 months and measures of monocyte inflammatory potential. If successful, the studies outlined in this proposal will extend the utility of Patiromer in high-risk diabetics at risk for future CV events and provide new information.

2.1 Preliminary Studies

RESEARCH STRATEGY

Pharmacological studies over > 20 years have defined the importance of the RAAS system in hypertension and heart failure. A number of trials have validated the use of MR antagonists in the management of patients with heart failure (RALES, EMPHASIS) and post myocardial infarction (EPHESUS)(1-4). Recent studies suggest that MR may link metabolic dysregulation with susceptibility to type II diabetes (T2DM) and atherosclerosis(5-12). MR is an ancient member of the 51-member, steroid-thyroid-retinoid receptor family. In response to ligand binding, MR undergoes conformational changes and is translocated to the nucleus where it binds to response elements in promoters, increasing transcription of target genes (13, 14). Despite its importance, the utilization of MR antagonists (MRAs) in clinical practice is abysmally low owing the perception that these agents cause excessive hypokalemia. Patiromer is a nonabsorbed anion polymer that exchanges a calcium-sorbitol counter ion for potassium cations in the GI lumen. Binding of free potassium in the GI tract leads to a decrease in serum potassium levels. Patiromer binds to 8.5 to 8.8 mEq of potassium per gram of polymer at a pH similar to that found in the colon and has a much higher potassium-binding capacity compared with other resins, including polystyrene sulfonate. In a series of Phase 2 and 3 clinical trials in patients with CKD, concomitant diabetes and heart failure, often necessitating concomitant therapies with RAAS blockers, Patiromer was shown to be effective in reducing potassium.(15-19) Recently Patiromer was shown to reduce aldosterone levels in patients receiving RAAS blockers suggesting that this strategy may be effective in lowering aldosterone levels in patients at risk and potentially providing a rationale to use this agent in patients Type 2 DM in conjunction with MR antagonists given the benefits of reducing MR activation articulated below. (Weir et al. Kidney International 2016. In press).

Cardiovascular Effects of MR Activation: MR is widely expressed in the cardiovascular system (20-23) and is a major determinant of endothelial function, smooth muscle tone, vascular remodeling, fibrosis and blood pressure (BP)(24-37). *In vitro*, animal, and human data support a role for MR activation in promoting vascular oxidative stress, inflammation, proliferation, migration, vasoconstriction, vascular remodeling and fibrosis (FIGURE. 1)(5, 29, 32, 37-45).

Similarly, MR antagonism is anti-inflammatory and antifibrotic with evidence in humans indicating reversal of endothelial dysfunction, diastolic dysfunction and vascular stiffness (46-50). The visceral adipose renin-angiotensin-aldosterone (RAS) system synthesizes aldosterone, expresses MR, and predicts IR in both humans and animal models (7, 51, 52). MR expression on macrophages could potentially play a pro-inflammatory role in

tissues such as adipose and vasculature.(53-56) MR blockade/deletion has been shown in both experimental and human studies to ameliorate IR (57-59). MR activation may affect IR through multiple mechanisms that include attenuation of insulin signaling in the heart, vasculature, and skeletal muscle. This may include impairment of expression of insulin receptor and substrate, decreased GLUT4 expression, abnormal phosphorylation of IRS, and activation of multiple stress kinases downstream of insulin receptor/IRS (leading to attenuation of insulin signaling)(60-63). MR activation also promotes hepatic oxidative stress, gluconeogenesis and enhances hyperglycemia (64). Recently, MR activation has been shown to promote lipid storage in brown adipose and inhibit UCP1 expression (65, 66). Consistent with these roles, MR antagonism in humans improves IR (57-59, 67). Relevant to this proposal we have provided evidence for a role for MR in pro-inflammatory macrophage phenotype and reduction in atherosclerosis in animal models. MR activation potentiates classical activation while deletion of MR or antagonism results in AΩ (68).

CV Trials in Type 2 DM: T2DM is recognized as a high-risk population for future CV events. However the risk is heterogenous with multiple factors determining risk in the diabetic. These factors include age, duration of diabetes, presence of concomitant risk factors, target organ damage and concomitant therapies including use of statins, RAAS blockers etc. It is widely felt that the presence of concomitant CKD characterizes a patient population at unusually high risk (right hand extreme of FIGURE 2) and this population presents many unique challenges. Importantly, very few therapies have been shown to be beneficial in preventing CV and renal disease progression. Angiotensin receptor blockers and possibly ACEI may reduce progression of renal disease and could potentially prevent occurrence of CV events although recent trials of RAS antagonism have been less conclusive than trials conducted 2 decades ago. There is good mechanistic data implicating continued activation of the RAAS cascade in diabetic CKD.(69) However trials of dual blockade or use of Renin inhibitors on top of ACEI/ARB have not been successful and have noted a higher incidence of mortality, hyperkalemia and hypotension.(69) One pathway that has been suspected to underlie the heightened risk posed by more complete RAAS blockade (defined as treatments that lower activation of the RAAS through the use of 2 or more agents such as an ACEI/ARB-MRA or ACEI/ARB+Renin inhibitor) is hyperkalemia.

[figure not shown]

FIGURE 2. Mortality rates in Type 2 DM trials. The highlighted trials are for dual RAS blockade that were terminated early owing to excess mortality noted with these studies.

Hyperkalemia with RAAS Therapy: High doses of angiotensin-converting enzyme inhibitors (ACEIs) or angiotensin II receptor blockers (ARBs), are recommended as first line treatment for diabetic nephropathy by various guidelines in light of their consistent cardioprotective role. Similarly there is emerging consensus that MRA on top of ACEI/ARB therapy may be beneficial as aldosterone typically is not completely suppressed. Indeed in HF patients and those with prior MI with LV dysfunction the guidelines do emphasize a Class I indication. However many patients especially diabetics with concomitant CKD are unable to tolerate these drugs particularly when given concomitantly. Effective hyperkalemia management with Patiromer may allow physicians to initiate and/or maintain optimal therapy with RAAS blockers. In the Phase II/III clinical trial experience with Patiromer, its co-administration with RAAS blockade safely and conveniently prevented RAAS-induced hyperkalemia and allowed full dose RAAS blockade to continue. A beneficial effect of the RAAS inhibitor was seen in reducing the level of proteinuria and blood pressure in patients with diabetes and renal disease. In the AMETHYST-DN trial effectively controlled serum potassium levels thereby allowing optimum treatment with RAAS inhibitors for up to one year. Indeed treatment with Patiromer reduced aldosterone levels and together with an MRA may allow complete inhibition of MR activation.

Patiromer Efficacy in CKD and Dosing Considerations: In the open-label AMETHYST-DN trial, reductions in serum potassium levels achieved with patiromer, persisted through 52 weeks of treatment.(15) In a continuation phase of the single-blind OPAL-HK trial, 107 patients whose serum potassium levels had fallen below 5.1 mEq/L after 4 weeks of treatment with patiromer were randomized to continue receiving the drug

or switch to placebo. The median increase in serum potassium levels after 8 weeks, the primary endpoint, was significantly greater in patients switched to placebo than in those who continued taking the active drug (0.72 vs 0.00 mEq/L). Patients who continued receiving patiromer were less likely to experience recurrent hyperkalemia than those switched to placebo (15% vs 60%) and more likely to remain on a RAAS inhibitor (94% vs 44%).(17) In another study in 25 patients with hyperkalemia and chronic kidney disease, patiromer 8.4 g twice daily significantly decreased serum potassium levels as early as 7 hours after administration of the first dose (-0.21 mEq/L). After 48 hours, mean levels had dropped by 0.75 mEq/L.(18) The Phase 3 studies confirm that the 16.8 g per day dose is reasonable in patients with mild hyperkalemia (defined as potassium concentration >5.0 to 5.5 mEq/L at baseline or at any time during dose titration) while a starting dose of 16.8 g/d is reasonable in patients with moderate hyperkalemia [potassium concentration >5.5 to <6.0 mEq/L]. The mean reduction in K⁺ with doses in AMETHYST-DN with this dose was 0.51 (95% CI, 0.38-0.64) mEq/L in the mild hyperkalemia group and 0.87 (95% CI, 0.60-1.14) mEq/L in the moderate hyperkalemia group.

Risk of Hypokalemia/Hypomagnesemia with Patiromer: In the PEARL-HF trial, the incidence of hypokalemia was 5% in the 30 g/d fixed dose group compared to 0% of the placebo group (titration of Patiromer was not allowed). The incidence of hypomagnesemia was 24% and 2% in the placebo group. In an open-label of Patiromer (RLY5016-204 trial), the starting dose of RLY5016 was 20 g/d and was titrated at weekly visits according to potassium level. With careful titration and follow-up, only one of 63 patients developed hypokalemia (serum K+<3.5), which was promptly reversed by decreasing the dose of Patiromer. Hypomagnesemia (serum Mg2+< 1.8 mg/dL) occurred in 8/63 (13%) of patients. In AMETHYST-DN, over the 52 week duration of the trial, hypomagnesemia (7.2%) was the most common treatment-related adverse event, with hypokalemia (<3.5 mEq/L) occurring in 5.6% of patients.

